1.2 Objectives

1. Primary Objective:
 - Photographic evaluation with correct identification of pre-treatment 2D images when compared to the 12 week follow up images performed by three independent reviewers.
2. Assessments:
 - Photographic evaluation with correct identification of pre-treatment 2D images when compared to the 4 week follow up images performed by three independent reviewers.
 - Photographic evaluation with Fitzpatrick Wrinkle Severity Scale (FWSS) grading comparing pre-treatment images to the 4 and 12 week follow up images performed by three independent reviewers.
 - Principle Investigator assessment using the Global Aesthetic Improvement Scale (GAIS) at the 4 and 12 week follow up visit.
 - Subject assessment using the Global Aesthetic Improvement Scale (SGAIS) at the 4 and 12 week follow up visit.
 - Subject Questionnaires
 - Pre-Treatment 1
 - Post Treatment 1
 - Follow Up
3. Safety Objectives:
 - Collection of Adverse Events
 - Collection of Treatment Discomfort/Pain Evaluation

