2.13 Evaluation Methods

Photographs:

Photographs will be taken at baseline and at the 4 and 12 week follow up visit, and may be taken at eat treatment visit to assess the efficacy and safety of treatment.

Treatment Discomfort/Pain Evaluation:

Subjects will be asked to report the general level of treatment discomfort on a scale of 0 (none) to 10 (maximum intolerable pain) using the universal pain assessment tool (Appendix B)

Fitzpatrick Wrinkle Severity Scale

The Fitzpatrick Wrinkle Severity Scale will be used to evaluate outcomes. Live evaluation will be performed at Baseline and the 4 and 12 week follow up visits. The results will be compared to determine improvement.

Class	Wrinkling	Score	Degree of Elastosis
I	Fine wrinkles	1-3	Mild (fine textural changes with subtly accentuated skin lines)
II	Fine to moderate-depth wrinkles, moderate number of lines	4-6	Moderate (distinct papular elastosis [individual papules with yellow translucency under direct lighting] and dyschromia)
III	Fine to deep wrinkles, numerous lines with or without redundant skin folds	7-9	Severe (multipapular and confluent elastosis [thickened yellow and pallid] approaching or consistent with cutis rhomboidalis)

Subject Treatment Questionnaire:

Subject treatment questionnaires may be collected from each subject to obtain feedback on their treatment experience.

Blinded Evaluation:

Three blinded independent reviewers will perform a photographic evaluation in which they will be asked to identify pre-treatment images when compared to post treatment images. The reviewers will be Board Certified Dermatologists and/or Surgeons and will be chosen based on availability and have relevant clinical experience. They will attend a training session prior to grading.

Physician and Subject Questionnaire:

The Global Aesthetic Improvement Scale (GAIS) ranging from “worse” to “very much improved” will be used to judge the improvement as seen by the subject and Investigator.

Global Aesthetic Improvement Scale Assessment	
Rating	Description
1	Very Much Improved- Optimal cosmetic result in this subject

2	Much Improved- Marked improvement in appearance from the initial condition, but not completely optimal for this subject.
3	Improved- Obvious improvement in appearance from initial condition, but a re-treatment is indicated.
4	No Change- The appearance is essentially the same as the original condition.
5	Worse- The appearance is worse than the original condition.

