2.14 Adverse Event Recording

All data captured must be supported by the Investigator’s timely assessment and documentation of the adverse event in the case report forms or source documents. All documented adverse events will be reviewed by the Sponsor or designee to determine whether the adverse event meets regulatory reporting requirements and to ensure timely adverse event reporting to meet local and global regulatory requirements. All adverse events must be followed until their resolution.

Adverse Events Pertaining to the TempSure Device:

Mild discomfort during treatment may be experienced by the subject. Typically, the discomfort is temporary and localized within the treatment area. Mild edema (swelling) and erythema (redness) may occur. Initial studies indicate that these side effects typically resolve within 2 to 24 hours.

Other anticipated side effects may include; pain, skin burns, bleeding, scarring, crusting, bruising, infection, itching, prolonged edema (swelling) and erythema (redness), hardness, and nodules. Loss of hair pigment may also occur within and adjacent to the treatment area.

Adverse Events Pertaining to the Icon Device:

Adverse effects can include discomfort/pain, redness, swelling, pinpoint bleeding, skin peeling, itching, scabbing, crusting, purpura, and bruising, which are usually transient and resolve without intervention.

Possible adverse effects include pustules (such as ingrown hairs), skin burns, hypopigmentation, hyperpigmentation, removal or lightening of freckles, scarring, infection and allergic reaction (such as a rash). There is also risk of incidental hair reduction or removal in the treated areas.

People of Middle Eastern and Mediterranean descent and those who have an ill-defined hair line with no obvious transition of the hairline to the face are at a high risk for hair stimulation (paradoxical hair growth).

Adverse Events Pertaining to Gel:

The gel is a water-based gel that may be placed on the skin during the TempSure® treatment. No known adverse events are documented. However, an allergic reaction is always possible when placing a topical gel onto the skin. Allergic reaction may include a mild reaction such as skin redness, irritation, or hives.

Adverse Events Pertaining to Neutral Pad:

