2.15 Statistical Analysis**2.15.1 Hypothesis**

For this study to be considered a success, of pre-treatment images when compared to post treatment (90 day) images will be $\geq 80\%$.

For the additional assessments to be considered a success, the following must be true:

- In cases where the subject's improvement is being graded on a scale, such as the FWSS and GAIS scale, we will test the statistical significance of our results against a hypothetical population that would have no change (average score of 4).
- Subject treatment and clinician usability questionnaires are collected.
- The side effect profile (adverse events) and the average pain score is acceptable to the Physician as it relates to the type of treatment.

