2.15.2 Sample Size Rationale

Based on the need for data collected from this study, it was determined that a total of 50 subjects will be required, including departures.

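### The 80% success criterion counts correct identification of the pre-treatment image and does not require the 12-week image to look better, so a pass alone shows visible change, not wrinkle improvement

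*Combined protocol and SAP*

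**What the plan says.** Section 1.2 gives the primary objective as "Photographic evaluation with correct identification of pre-treatment 2D images when compared to the 12 week follow up images performed by three independent reviewers". The Blinded Evaluation paragraph of section 2.13 describes the task: "Three blinded independent reviewers will perform a photographic evaluation", in which "they will be asked to identify pre-treatment images when compared to post treatment images". It mentions a training session but not its content.

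The success rule in section 2.15.1 reads "For this study to be considered a success, of pre-treatment images when compared to post treatment (90 day) images will be" at least 80%. That sentence has lost its subject; read with section 1.2, the subject is the rate of correct identification.

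Direction of change is recorded in other places. Section 1.2 lists, among the further assessments, FWSS grading of the photographs by three independent reviewers at 4 and 12 weeks, and GAIS ratings by the investigator and the subject. The GAIS in section 2.13 has a category for a worse appearance. Adverse events are assessed at Visits 6 and 7 (section 2.12) and summarised descriptively (section 2.15.6). None of these enters the 80% rule.

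Section 2.14 lists less common TempSure effects that may occur, including "skin burns, bleeding, scarring, crusting, bruising, infection, itching, prolonged edema (swelling) and erythema (redness), hardness, and nodules". For Icon it adds lightening and darkening of the skin and scarring.

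**The concern.** Section 1.1 states the purpose as efficacy for facial wrinkles, and section 2.1 says the data are to support marketing claims. The primary endpoint asks a different question: can an expert tell which photograph came first? Fewer wrinkles is one reason the two images might differ. A scar, a nodule or a pigment change is another, and an experienced dermatologist or surgeon may recognise it as a consequence of treatment and so name the other image as the earlier one. That read is scored correct and counts towards 80%.

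Standardised photography under section 13.0 does not remove this, because the mark is a real difference between the faces. What is at stake is the meaning of a pass: it establishes that the images are distinguishable and leaves open in which direction.

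**Working it through.** **Is direction part of the criterion?** Section 1.2 defines the outcome as identification. Section 2.13 gives the reviewers an identification task and no better-or-worse question within it. Section 2.15.1 applies the threshold to identification. No section scores a correctly identified but worsened subject as a failure, and no section tells reviewers to treat the worse-looking image as the earlier one. On the text, direction is not part of the criterion.

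**Inputs from the documents.** N = 50 (section 2.15.2: "it was determined that a total of 50 subjects will be required, including departures"); threshold 80%, so 0.80 × 50 = 40 subjects. The figure of 50 cannot be reproduced, because no error rate, power, null rate or expected rate is given.

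**Assumptions, not in the documents.** All 50 subjects are evaluable, with one correct-or-incorrect result each (the plan has no rule for combining three reviewers). Unharmed subjects are identified with probability p = 0.75. A fraction h of subjects has visible harm at 12 weeks, and these are identified with probability c.

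**Formula.** Overall rate = p(1 − h) + hc. The chance of passing is the exact binomial probability of at least 40 of 50 at that rate.

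| h | c | Overall rate | P(≥ 40 of 50) |
|---|---|---|---|
| 0 | – | 0.75 | 0.262 |
| 0.05 | 1.00 | 0.75 × 0.95 + 0.05 × 1.00 = 0.7625 | 0.333 |
| 0.20 | 1.00 | 0.75 × 0.80 + 0.20 × 1.00 = 0.80 | 0.584 |
| 0.20 | 0.75 | 0.75 × 0.80 + 0.20 × 0.75 = 0.75 | 0.262 |
| 0.20 | 0.50 | 0.75 × 0.80 + 0.20 × 0.50 = 0.70 | 0.079 |
| 0.20 | 0.05 | 0.75 × 0.80 + 0.20 × 0.05 = 0.61 | 0.003 |

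Harm raises the pass probability only when c exceeds p. Below that it lowers it.

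**A second illustration, splitting subjects by outcome.** Take 30 improved (identified with probability 0.95), 10 unchanged (0.50) and 10 worsened (c). The expected rate is (28.5 + 5 + 10c)/50.

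- c = 0.05: 34/50 = 68%, P(≥ 40) = 0.003
- c = 0.50: 38.5/50 = 77%, P(≥ 40) = 0.351
- c = 0.95: 43/50 = 86%, P(≥ 40) = 0.949

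The wrinkle outcomes are the same in all three lines. Only the way reviewers read worsened faces differs, and the protocol leaves that open. The proportion both correctly identified and improved is 28.5/50 = 57% in each line.

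Pure guessing (rate 0.50) gives P(≥ 40) of about 0.00001, so the threshold guards against guessing. It does not guard against recognisable change in an unwanted direction.

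**The case against.** There are four serious replies.

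1. *Direction is already collected.* Section 1.2 plans photographic FWSS grading by three independent reviewers at the same visit, GAIS can record worsening, and section 2.15.1 asks that the side-effect profile be acceptable to the physician. A pass driven by harm should show in the study's own outputs. This stands as far as it goes. However, these results sit outside the 80% rule, and the planned group summaries do not show whether the subjects counted as successes are the ones who improved.

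2. *Reviewers expecting benefit will call the worse image the earlier one.* For worsened wrinkling alone this is plausible, and such subjects would then count against success, as the low-c rows show. It is less convincing for a mark that looks treatment-related. It also rests on an expectation that the plan does not state.

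3. *Most visible effects will have gone by 12 weeks.* Section 2.14 says common TempSure effects typically resolve within 2 to 24 hours and describes the first group of Icon effects as usually transient. A reader might infer from the longer list that visible harm at 12 weeks is expected. The documents do not support that: the list is of effects that may occur, without rates and mostly without durations.

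4. *A redefined primary endpoint at the same threshold would be a much harder test.* This is right. The threshold was set for identification, and the second illustration falls from 86% to 57% at c = 0.95.

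A reader might also infer that the criterion is likely to be met through harm, or that harm always helps the sponsor. Neither follows, since both h and c are unknown.

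**Conclusion.** The point holds as a limit on interpretation. The 80% criterion can count a subject who was recognised by an unwanted visible effect, and a pass alone shows visible change, not wrinkle improvement. This rests on the wording of sections 1.2, 2.13 and 2.15.1 and needs no numerical assumption.

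The size and sign of any effect on the pass probability cannot be determined. Under the assumed 75% base rate and 20% harm, it ranges from an increase (0.26 to 0.58 with certain recognition) to a decrease (0.26 to 0.08 at even odds, lower still if reviewers take the worse image as the earlier one). At 5% harm with certain recognition the change is small (0.26 to 0.33), and with no visible harm at 12 weeks it is nil. The documents do not support a claim that the endpoint is biased in the sponsor's favour.

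**What to change.** In section 2.13, add one item to each blinded pair read: which image shows less wrinkling (left, right, or no difference). Alternatively, use the photographic FWSS grading already listed in section 1.2. In that case, state that it is read from photographs blind to visit, and reconcile it with section 2.13, which describes FWSS as a live evaluation.

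In section 2.15.1, restore the missing subject of the success sentence and report the following beside the identification rate:

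- the proportion of subjects both correctly identified and rated less wrinkled at 12 weeks;
- the number correctly identified but rated unchanged or worse, or with an ongoing adverse event in the treated area at Visit 7.

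State how the three reviewers' answers combine into one result per subject for both rates. Base any claim of wrinkle improvement on the joint proportion.

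The cost is a little more reading and analysis, with the same reviewers, the same images and no extra visit. The joint rate may be materially lower than the identification rate. Whether to make it the primary endpoint, and at what threshold, is the sponsor's choice; this point does not require it.

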2.14 Adverse Event Recording

All data captured must be supported by the Investigator’s timely assessment and documentation of the adverse event in the case report forms or source documents. All documented adverse events will be reviewed by the Sponsor or designee to determine whether the adverse event meets regulatory reporting requirements and to ensure timely adverse event reporting to meet local and global regulatory requirements. All adverse events must be followed until their resolution.

Adverse Events Pertaining to the TempSure Device:

Mild discomfort during treatment may be experienced by the subject. Typically, the discomfort is temporary and localized within the treatment area. Mild edema (swelling) and erythema (redness) may occur. Initial studies indicate that these side effects typically resolve within 2 to 24 hours.

Other anticipated side effects may include; pain, skin burns, bleeding, scarring, crusting, bruising, infection, itching, prolonged edema (swelling) and erythema (redness), hardness, and nodules. Loss of hair pigment may also occur within and adjacent to the treatment area.

Adverse Events Pertaining to the Icon Device:

Adverse effects can include discomfort/pain, redness, swelling, pinpoint bleeding, skin peeling, itching, scabbing, crusting, purpura, and bruising, which are usually transient and resolve without intervention.

Possible adverse effects include pustules (such as ingrown hairs), skin burns, hypopigmentation, hyperpigmentation, removal or lightening of freckles, scarring, infection and allergic reaction (such as a rash). There is also risk of incidental hair reduction or removal in the treated areas.

People of Middle Eastern and Mediterranean descent and those who have an ill-defined hair line with no obvious transition of the hairline to the face are at a high risk for hair stimulation (paradoxical hair growth).

Adverse Events Pertaining to Gel:

The gel is a water-based gel that may be placed on the skin during the TempSure® treatment. No known adverse events are documented. However, an allergic reaction is always possible when placing a topical gel onto the skin. Allergic reaction may include a mild reaction such as skin redness, irritation, or hives.

Adverse Events Pertaining to Neutral Pad:

Mild heat or hot spots may be felt during treatment by the subject. If the subject reports heat at the pad site, evaluate the site, check for epidermal injury. Skins burns may occur if subject does not report if the pad becomes too hot.

Adverse Events Pertaining to Cooling:

Anticipated transient side effects associated with forced air/contact cooling may include tingling, itching, decreased sensation, numbness, redness and pain.

Adverse Events Pertaining to the Surgical Marker:

Using surgical marker has minimal risks and may produce effects on the body such as redness or a rash. Markings may remain visible for a few days or may be removed with alcohol.

Other Cautions:

Incomplete response or no response may occur since some subjects may not respond to treatment.

2.15 Statistical Analysis**2.15.1 Hypothesis**

For this study to be considered a success, of pre-treatment images when compared to post treatment (90 day) images will be $\geq 80\%$.

For the additional assessments to be considered a success, the following must be true:

- In cases where the subject's improvement is being graded on a scale, such as the FWSS and GAIS scale, we will test the statistical significance of our results against a hypothetical population that would have no change (average score of 4).
- Subject treatment and clinician usability questionnaires are collected.
- The side effect profile (adverse events) and the average pain score is acceptable to the Physician as it relates to the type of treatment.

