1.0 PURPOSE

1.1 Name and Intended Use

The device used in this study is called the TempSure device. The study will be using the Mini Envi handpiece and may also use the Envi handpieces and Icon device (Max series).

The intended use of the TempSure device used in this study to assess the efficacy of the handpiece for the treatment of facial wrinkles. If the Icon device is used, the intended use will be for the treatment of benign pigmented and/or vascular lesions.

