2.0 PROTOCOL

2.1 Protocol Methodology and Analysis

Methodology:

Subjects are to be enrolled in this clinical study if they are a healthy male or female 18 years of age or older. Up to 50 subjects will be enrolled at 3 study centers. Subjects will be enrolled into 2

groups, Group A for TempSure treatments only and Group B for TempSure and Icon treatments. Randomization will not be required as subjects will only be enrolled in Group B and treated with the Icon device if they present with pigment and/r vascular lesions. Subjects will attend a screening/pre-treatment visit which may be performed on the same day as the treatment visit. Subjects in Group A will receive up to 4 treatments with the TempSure device on the face. Subjects in Group B will receive 2 treatments with just the TempSure device and 2 treatments with both the TempSure and Icon device. Some subjects may be asked to return for an optional 5th treatment (2 – 3 weeks post last treatment) with the Icon device (and/or TempSure device) after the completion of their 4 treatments at the discretion of the Investigator. Subjects may receive a phone call 1 week (1-7 days) after each treatment to record side effects. Subjects will return for follow up visits at 4 and 12 weeks post last treatment for efficacy and side effects assessments. An unscheduled visit or phone call may be performed at any time during the study at the request of the subject or as deemed necessary by the site Investigator.

Analysis:

Upcoming generations are proving to have an interest in non-ablative aesthetic treatments and will drive demand for innovated products, procedures, and practice design.¹ Due to this shift in patient base, practices need to evolve to adapt to the newer generational ideologies. There have been rapid advances in RF technology over the past few years and the nonsurgical treatment using this energy source offers great promise to our aging population.² Radiofrequency technology for the treatment facial wrinkles and skin laxity needs to be further investigated to optimize treatment parameters for safe and effective non-ablative aesthetic treatments.

Relevance:

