2.8 Post Treatment Procedures

- Adverse events will be documented after treatment.
- Photographs may be taken post treatment.
- After treatment 1 only, subjects will be asked to complete a Post Treatment 1 Questionnaire.
- The following post treatment instructions will be reviewed:
 - If the skin is slightly pink or red in areas following the treatment, avoid hot water when washing or showering until any erythema (redness) has subsided.
 - Soothing creams or moisturizers, such as Aveeno, may be used.
 - Gently massage the treated area daily for 5 minutes for the duration of your involvement in the study.
 - Use a sun block with UVA and UVB protection with SPF of 30 or greater to prevent sun damage.
 - Maintain the same weight and exercise routine throughout the study.
- If the subject is treated with the Icon device, the following post treatment instructions will also be reviewed:
 - A mild sunburn-like sensation is expected. This usually lasts two to twenty-four (2-24) hours but can persist up to seventy-two (72) hours. Mild swelling and/or redness may accompany this, but it usually resolves in two to three (2-3) days. Apply wrapped ice or gel packs to the treatment area for ten to fifteen (10-15) minutes every hour for the next four hours, as needed. Never apply ice directly to skin. An oral, over-the-counter anti-inflammatory (ibuprofen such as Advil®) or an analgesic (acetaminophen such as Tylenol®) may be taken to reduce discomfort. Use medicine according to manufacturer's recommendations.
 - Until redness has resolved, it is recommended to avoid the following:
 - Applying cosmetics to treated areas.
 - Swimming, especially in pools with chemicals, such as chlorine.
 - Hot tubs, Jacuzzis, and saunas.
 - Activities that cause excessive perspiration or any activity that may raise core body temperature.
 - Sun exposure and tanning in treated areas. Apply a SPF 45 or greater sunscreen to prevent skin color changes.
 - Aggressive scrubbing and use of exfoliants on the treated area.
 - Bathe or shower as usual. Treated areas may be temperature-sensitive.

- Pigmented lesions may initially look raised and/or darker with a reddened perimeter.
- Pigmented lesions will gradually turn darker over the next twenty-four to forty-eight (24-48) hours. It may turn dark brown or even black.
- Pigmented lesions will progress to darkening and/or crusting and will start flaking off in an average of seven to twenty-one (7-21) days.

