- Vascular lesions may undergo immediate graying or blanching, or they may exhibit a slight purple or red color change. The vessels will fully or partially fade in about ten to fourteen (10-14) days.
- Do not pick or pull at darkened lesions as scarring may occur.

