2.12 Schedule of Visits and Procedures

	Visit #1*	Visit #2 - 5	Treatment Visit*** (Optional)	Call (Optional)	Visit #6	Visit #7
Procedure	Screening and Pretreatment Procedures	Treatment Visits 1-4 (1 - 2 weeks apart)	Treatment Visit #5 (2 - 3 weeks post last treatment)	Phone Call 1 Week Post Each Tx (1-7 Days)	Follow Up 4 Weeks Post Last Tx (+/- 1 Week)	Follow Up 12 Weeks Post Last Tx (+/- 1 Week)
Medical History	X					
Pregnancy Verification**	X	X	X			
Informed Consent	X					
Photographs	X	X	X		X	X
FWSS	X				X	X
Subject Pre-Treatment 1 Questionnaire		X				
Treatment		X	X			
Treatment Discomfort/ Pain Evaluation		X	X			
Subject Post Treatment 1 Questionnaire		X				
PGAIS					X	X
SGAIS					X	X
Subject Follow Up Questionnaire					X	X
Adverse Events Assessment	X	X	X	X	X	X

*Screening and Pretreatment Procedures may occur at the same time as the first Treatment Visit.

**Pregnancy verification required before each treatment only for women of childbearing potential.

***Group B only

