2.15.3 Patient Populations

Interim results may be collected and reported. All data will be analyzed at the end of the study. The primary analysis will be performed by the intention-to-treat approach. Everyone who begins the treatment is part of the study whether he or she completes the study or not. Additional per-protocol analysis may also be performed on subjects who complete the entire clinical trial according to the protocol. The most appropriate method of handling missing values will be chosen based on the individual trial goals, endpoints and context.

The analysis of demographic, medical history, and efficacy variables will be based on all patients who are randomized and receive at least one treatment. The analysis of safety data will be based on all patients who are randomized, receive at least one treatment, and have at least some safety data.

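### The 80% photo-identification criterion names no group, so a pooled pass that includes Icon-treated Group B cannot by itself be attributed to TempSure's effect on wrinkles

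*Combined protocol and SAP*

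**What the plan says.** The success rule in Section 2.15.1 reads "For this study to be considered a success, of pre-treatment images when compared to post treatment (90 day) images will be" at least 80%. Its grammatical subject is missing from the text as available. The primary objective in Section 1.2 supplies it: "Photographic evaluation with correct identification of pre-treatment 2D images when compared to the 12 week follow up images performed by three independent reviewers". Neither place names a group.

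Section 2.15.3 makes the primary analysis intention-to-treat: "Everyone who begins the treatment is part of the study whether he or she completes the study or not".

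Section 2.1 defines Group A as TempSure only and Group B as TempSure plus Icon, without randomization: "subjects will only be enrolled in Group B and treated with the Icon device if they present with pigment and/r vascular lesions". No group sizes are given.

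Section 1.1 separates the purposes. For TempSure it says "The intended use of the TempSure device used in this study to assess the efficacy of the handpiece for the treatment of facial wrinkles"; for Icon it names benign pigmented and/or vascular lesions.

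Section 2.8 tells Icon-treated subjects what to expect: "Pigmented lesions will progress to darkening and/or crusting and will start flaking off in an average of seven to twenty-one (7-21) days", and for vascular lesions, "The vessels will fully or partially fade in about ten to fourteen (10-14) days". The primary photograph comes later; the schedule in Section 2.12 has "Follow Up 12 Weeks Post Last Tx (+/- 1 Week".

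Under Section 2.13 three blinded reviewers are asked to pick out the pre-treatment image. They attend a training session, but nothing there ties the choice to wrinkles.

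**The concern.** Group B subjects are chosen because they have visible lesions, and they are treated with a device meant to clear them. A reviewer can then pick the earlier photograph correctly because a brown spot or vessel has gone, whatever happened to the wrinkles. Blinding and standardized photography do not remove that cue, because it is in the skin.

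If both groups count towards one 80% figure, an easily identified Group B could carry a weak Group A result over the line. If Group B is harder to identify, a good Group A result could be pulled under it. Without rates by group, a reader of the report could not tell which had happened. At stake is whether the study's one primary success statement says anything specific about TempSure and wrinkles.

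**Working it through.** **1. Does the plan separate the groups for this endpoint?** Sections 1.2 and 2.15.1 name no group, and Section 2.15.3 counts everyone who begins treatment. By-group analysis appears in Section 2.15.4 (demographics and history), Section 2.15.5 (efficacy) and Section 2.15.6 (safety). Section 2.15.5 opens with the additional variable, change from baseline, and prescribes means, a mixed model and paired t-tests. These fit change scores, not a correct/incorrect result.

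**2. Is the lesion cue present by the time of the photograph?** The earliest scheduled primary photograph is 12 − 1 = 11 weeks, or 77 days, after the last treatment; the latest is 13 weeks. Pigmented lesions are expected to start flaking off at 7–21 days and vessels to fade fully or partially at about 10–14 days. Both ranges end well before day 77.

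**3. How much could pooling matter?** Section 2.15.2 gives 50 subjects in total with no calculation behind it, so there is no power figure to reproduce. The documents give no group sizes and no identification rates. Everything below is therefore assumed: a two-image choice (50% by chance), one correct/incorrect result per subject (no rule combines the three reviewers), independent subjects and 50 evaluable. A pass is 0.80 × 50 = 40 or more correct.

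*Break-even.* The pooled rate is exactly 80% when pA = (40 − nB·pB)/(50 − nB). With pB = 90%, pA is 77.5% for nB = 10, (40 − 18)/30 = 73.3% for nB = 20 and (40 − 22.5)/25 = 70.0% for nB = 25. With pB = 100% it is 75.0%, 66.7% and 60.0%.

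*Exact pass probability.* P(pass) = Σₐ P[Bin(50 − nB, pA) = a] × P[Bin(nB, pB) ≥ 40 − a].

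Group A truly at 60%:

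| nB | pB 80% | pB 90% | pB 98% | Group A alone, at least 80% |
|---|---|---|---|---|
| 10 | 1% | 2% | 3% | 0.6% (32/40) |
| 20 | 4% | 12% | 25% | 1.7% (24/30) |
| 25 | 7% | 25% | 51% | 2.9% (20/25) |

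Group A at chance (50%):

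| nB | pB 80% | pB 90% | pB 98% |
|---|---|---|---|
| 10 | <0.1% | <0.1% | 0.1% |
| 20 | 0.4% | 1.5% | 3.9% |
| 25 | 1% | 6% | 17% |
| 30 | 4% | 18% | 49% |

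*No inflation.* With Group A at 60% and Group B at 70%, the pooled pass probability is 0.5%, 1% and 2% for nB = 10, 20 and 25, no higher than Group A alone.

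*Reverse direction.* With Group A at 90% and Group B at 70%, the pooled rule passes 72% of the time with nB = 20 and 58% with nB = 25. Group A alone would pass 97% of the time in both cases.

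*Fewer evaluable subjects.* Section 2.15.2 counts departures within the 50. With 45 evaluable (pass = 36), Group A at 60% and 18 in Group B (40%), the figures are 5% / 14% / 27%, close to the nB = 20 row.

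**The case against.** Pooling is inferred, not stated. Section 2.15.3 says who is counted; it does not forbid results by group. Section 2.15.5 is unclear: it mentions the primary efficacy variable and asks for summaries by treatment group, so someone could say that by-group reporting is already planned. Its methods do not suit a binary endpoint, but the wording leaves room. Group membership is recorded, so rates by group could be computed later. What would be lost is pre-specification.

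The 80% rule is also not labelled a TempSure-only claim. Sections 1.1, 2.2 and 3.3 cover both devices and both conditions, so the rule can fairly be read as a criterion for the regimen each subject received. That stands, and it is why the point concerns attribution and not the validity of the rule as such. The Fitzpatrick Wrinkle Severity Scale (FWSS) gives wrinkle-specific evidence, but it is an additional assessment and does not enter the 80% rule.

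A reader might infer that Icon treatment must inflate the result. The documents do not support that. Section 2.14 lists hyperpigmentation, which could make the later image look worse, and warns of incomplete or no response, which would weaken the cue. Success is the probable direction, not a certain one.

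A reader might also infer that Group A must be the sole basis for success. That goes too far: nothing guarantees Group A's size, and a bare 80% point estimate is easier to reach on a weak effect in a small group. At a true rate of 70%, the chance of observing at least 80% is 8% with 50 subjects, 16% with 30 and 24% with 20.

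**Conclusion.** The concern holds as a matter of attribution. As written, the natural reading gives one pooled identification rate, and a pass on it cannot by itself be credited to TempSure's effect on wrinkles. A pooled failure could equally mask a good Group A result. A pass would not show that TempSure had no effect: Group B also receives TempSure, and its correct identifications cannot be divided between the devices.

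The size rests wholly on assumed shares and rates. With about 10 of 50 subjects in Group B the effect is negligible (at most 3% with Group A at 60%). With Group A at 60%, it becomes large only when Group B is about 40% or more of subjects and is identified about 90% of the time or more. With Group A at chance, Group B must be larger still. The documents do not limit Group B's share, so neither case can be excluded.

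**What to change.** In Section 2.15.1, pre-specify three things:

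- The 12-week identification rate is reported with an exact 95% confidence interval for Group A, Group B and pooled.
- A pooled or Group B pass is described as a result for the regimens received.
- Any TempSure-only wrinkle statement from this endpoint cites the Group A rate with its interval, not the bare 80% point estimate.

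In the reviewer training already planned in Section 2.13, instruct reviewers to base the pre/post choice on wrinkles. This is only a partial safeguard, because cleared lesions stay visible in the images. Leave FWSS grading unchanged, since its descriptors include dyschromia.

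The cost is a few sentences and one training instruction, with no new visits, images or data. The statistical price is precision: at an observed 80%, the exact 95% interval is 59–93% with 25 in Group A, against 66–90% with 50. Because a small group passes a point-estimate rule more easily on a weak effect, the interval has to accompany the rate. A Group A result would still have no untreated control; separating the groups removes only the Icon lesion cue.
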